#### **11.4.1.4. Coding**

Medical history, AEs, concomitant treatments and/or procedures, and surgeries will be coded per SOC and PT using the last available version of the Medical Dictionary for Regulatory Activities (MedDRA). Past and concomitant medications will be coded per anatomical therapeutic chemical (ATC) class levels 2 and 4 using the last available World Health Organization (WHO) Drug Dictionary.

### **11.5. Selection of patients for statistical analysis**

#### **11.5.1. RP2D population (part A only)**

Patients will be considered as not evaluable for DLTs and excluded from the RP2D population, if they did not receive at least 70% of Debio 1143 (i.e., a maximum of 6 missed Debio 1143 doses) and at least one nivolumab dose as planned in Cycle 1 for any reason other than DLT.

Patients not evaluable for DLT will be replaced if there are less than 3 evaluable patients by cohort.

If a treatment modification during the DLT period leads to a potentially non-evaluable patient, the final decision regarding the patient's evaluability will be taken only at the end of his/her DLT period. If the patient experiences a DLT, he/she will be considered as evaluable regardless his/her exposure.

#### **11.5.2. Safety population**

The safety population is defined as enrolled patients who received at least one dose of any study drug.

#### **11.5.3. ITT population**

The intention-to-treat (ITT) population will include all enrolled patients who took at least one dose of any study drug. This is to exclude the patients who took no trial medication. Therefore, the ITT population is identical with the current Safety population.

#### **11.5.4. Efficacy population**

The efficacy population is defined as patients who have:

- measurable disease according to RECIST v1.1 and/or GCIG criteria (Cohort 4, if applicable) and
- a baseline tumor assessment and at least one post-baseline tumor assessment, either CT or MRI for RECIST evaluable patients, or CA-125 dosage performed after baseline, if applicable, or
- treatment discontinuation occurred before the efficacy assessment was done due to treatment failure, defined as: death, unacceptable toxicity, clinical deterioration and/or symptoms worsening

Patients with treatment failure will not be replaced and will be included in the efficacy population.

In case of non-permitted concomitant treatments or critical protocol violations that may affect the patient benefit/risk balance (i.e., non-eligibility criteria), efficacy data assessed after such protocol violations will be excluded from the efficacy analysis, as appropriate, but the patient will be kept in the efficacy population. This will be described in detail in the statistical analysis plan (SAP).

## 11.6. Statistical analysis

The statistical analysis described below corresponds to what is foreseen during the planning of this study. If during the study, circumstances should arise that render this analysis inappropriate, or if in the meantime improved methods of analysis should come to light, a different analysis may be performed. Therefore, the definitive statistical analysis will be described in the SAP. Any deviations from this plan, reasons for such deviations, and all alternative or additional statistical analyses that may be made, will be described in the final report.

Ordinal and continuous data will be presented, in the form of descriptive statistics, as number of patients, mean, standard deviation, minimum, median, maximum, and 95% confidence interval (CI). In addition, for PK parameters (see section 11.6.4.5), the geometric mean, 90% CIs of geometric means, the standard deviation of the geometric means, and geometric coefficient of variation (CV%) will be presented if applicable. Categorical data will be presented, using contingency tables with absolute and relative frequencies.

For Part A, the results will be reported overall and by dose, while for Part B, the results will be reported by cohort and overall (except for efficacy in case of heterogeneous data and futile cohorts).

All data analyses will be performed using the statistical softwares SAS®, R, NONMEM®, and Phoenix™ WinNonlin®.

### 11.6.1. Part A

Due to the nature and design of the study, the statistical analysis of the dose-optimization part will be mostly descriptive unless otherwise specified.

### 11.6.2. Part B

Part B of the study is an exploratory basket trial intended to assess the preliminary efficacy of Debio 1143 in combination with nivolumab in four indications and promising efficacy results should be further evaluated in subsequent trials. Due to the exploratory nature of the trial, there will be no formal hypotheses testing.

Bayesian posterior probability will be used for the early stopping rules for futility and to assess the efficacy. The claim of efficacy will be based on the primary endpoint (confirmed ORR), while the futility stopping rules will use the unconfirmed ORR.

Recruitment will be stopped in the futile cohorts. A homogeneity test will be conducted in the non-futile cohorts showing a confirmed response rate of at least 15%. In case of homogeneous response rates across the cohorts, efficacy data will be pooled and all the efficacy endpoints will be reported overall and by cohort. Otherwise, the efficacy will be reported by cohort only. The efficacy of the futile cohorts and of the cohorts with less than 15% response rate will be reported separately.

All other endpoints such as demographics, baseline characteristics, safety, PK, PDy, etc. will be presented overall and for each cohort.

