#### 4.1.2. Part B

The primary objective of the basket trial is to evaluate the preliminary anti-tumor activity of Debio 1143 at the RP2D in combination with nivolumab at the standard dose, overall and in each patient cohort.

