### 5.1.2. Part B

Part B is a multicenter, open-label, basket trial using Debio 1143 in combination with nivolumab at the RP2D as previously defined in Part A, in patients with advanced/unresectable solid tumors. Eligible patients will be simultaneously included into four cohorts according to tumor type:

- **Cohort 1:** SCLC (including extrapulmonary small-cell carcinomas or large cell neuroendocrine lung carcinoma, as per WHO Classification of Lung Tumors of 2015 (34))
- **Cohort 2:** SCCHN (nasopharyngeal carcinomas are excluded)
- **Cohort 3:** GI cancers, including esophageal, gastric, colorectal or pancreatobiliary tumors, with known MSI-H/ MMRd or other known DDRs abnormalities (incl. HRD).
- **Cohort 4:** platinum-resistant EOC), endometrial cancer, PPC and cervical cancer, with known MSI-H/ MMRd, hereditary/somatic mutations of the BRCA1 and BRCA2 genes or other known DNA DDRs abnormalities (incl. HRD).

The primary objective of Part B is to assess whether the combination of Debio 1143 with nivolumab is active overall and in each cohort. Early futility stopping rules based on ORR (unconfirmed) will be used. In each cohort, if no unconfirmed response is observed according to Response Evaluation Criteria in Solid Tumors (RECIST v1.1) or Gynecologic Cancer Intergroup (GCIIG) criteria (Cohort 4, if applicable) once the initial 8 evaluable patients have been assessed at least twice after baseline or have discontinued their treatment earlier, futility will be concluded and recruitment will be stopped in that cohort. If at least one response (unconfirmed) is documented in the initial 8 evaluable patients, recruitment shall continue up to 11 evaluable patients. At least two unconfirmed responses must then be observed in these 11 evaluable patients to continue the recruitment up to 15 evaluable patients in that cohort.

A homogeneity test will be conducted in any non-futile cohorts showing a confirmed response rate of at least 15%. If homogeneous response rates are seen across the cohorts, efficacy data will be pooled and an overall efficacy analysis will be conducted in addition to the analyses by cohort. For the final efficacy assessment, first proof of efficacy will be claimed in a given cohort if at least 4 confirmed objective responses are reported in the 15 evaluable patients.

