### 11.6.4. Final analysis

The final analysis will be performed within one year of the End of the Main study period (which lasts until 18 months after LPI or 60 days after last LPLV, whichever occurs first).

Data collected after the Main study period for patients entering the Extended study period, will be summarized using descriptive statistics and included in an addendum to the Final CSR.

The main study results will be presented separately for both study parts. An exploratory analysis will be conducted by pooling demographics, baseline characteristics and safety, data from both study parts. In addition, if homogeneity tests allow, and any specific cohort population is adequately represented in Part A, efficacy data from both study parts may be pooled exploratory, as appropriate.

In Part B, according to the Bayesian posterior probability used in each non-futile cohort at the final efficacy assessment conducted in the 15 evaluable patients, the first proof of efficacy will be claimed if at least four confirmed responses are reported in these 15 evaluable patients. This efficacy boundary was derived assuming a confirmed ORR of 15% and a probability confidence threshold of efficacy of 80%.

A homogeneity test of the primary endpoint will be conducted in the non-futile cohorts showing a confirmed response rate of at least 15%. In case of homogeneous response rates across the cohorts, efficacy data will be pooled and all the efficacy endpoints will be reported overall and by cohort. Otherwise, the efficacy will

be reported by cohort only. The efficacy of the futile cohorts and of the cohorts with less than 15% response rate will be reported separately.

All other endpoints such as demographics, baseline characteristics, safety, PK, PDy, etc. will be presented overall and for each cohort.

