9. OUTPUT PRESENTATIONS

Appendix 1 shows conventions for presentation of data in outputs.

The templates provided with this SAP describe the presentations for this study and therefore the format and content of the summary tables, figures, and listings to be provided by IQVIA Biostatistics.

All endpoints such as demographics, baseline characteristics, safety, PK, PDy, etc. will be presented overall and by dose level for Part A and cohort for Part B.

All outputs will be presented for both Part A and Part B separately.

For Part B, the efficacy outputs will be reported by cohort.

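### Part B's primary objective covers overall activity, but the only planned overall confirmed ORR pools cohorts already selected for an observed rate of at least 15%

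*Protocol*

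**What the plan says.** **Objective.** Protocol 4.1.2 sets out to evaluate the activity of "Debio 1143 at the RP2D in combination with nivolumab at the standard dose, overall and in each patient cohort". Protocol 5.1.2 repeats it: "The primary objective of Part B is to assess whether the combination of Debio 1143 with nivolumab is active overall and in each cohort".

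**Rule for an overall estimate.** Protocol 11.6.2: "A homogeneity test will be conducted in the non-futile cohorts showing a confirmed response rate of at least 15" per cent. It goes on (the quote stops one word short, where the single cohort is named as the second level of reporting): "In case of homogeneous response rates across the cohorts, efficacy data will be pooled and all the efficacy endpoints will be reported overall and by". If not homogeneous: "Otherwise, the efficacy will be reported by cohort only". Protocol 11.6.4.3 specifies a Fisher exact test at the 0.3 level, and a one-sided exact binomial interval (alpha 0.05) for the pooled rate.

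**What stays out.** Protocol 11.6.4: "The efficacy of the futile cohorts and of the cohorts with less than 15% response rate will be reported separately". The introduction to Protocol 11.6 states the matching exception to overall reporting: "except for efficacy in case of heterogeneous data and futile cohorts".

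**SAP.** Section 17.1.3 keeps the same rule but glosses the 15% filter as at least 4 responders, and replaces the interval with a two-sided 95% credible interval from the beta posterior. SAP section 9 says: "For Part B, the efficacy outputs will be reported by cohort". SAP 4.3 gives the futility of the Part B cohorts as the reason for not pooling Part A with Part B.

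Neither document defines a confirmed ORR over all evaluable Part B patients, and neither adjusts the pooled estimate for how its cohorts were chosen.

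**The concern.** Half of the primary objective is about the basket as a whole, but the estimate meant to address it is taken only from cohorts that have already done well on the same endpoint in the same patients. Low cohorts are removed before homogeneity is tested, so the test cannot show that the basket as a whole is mixed. The pooled point estimate also cannot fall below 15%, the confirmed rate that Protocol 11.6.3 calls promising enough for further development.

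Two things are at stake. If a pooled rate is reported, it is biased upward as a statement about the four-cohort basket, and nothing in the plan requires it to be labelled as selected. If too few cohorts qualify, the overall part of the objective gets no estimate, although the patients have been treated and assessed.

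**Working it through.** **Inputs from the documents.** Four cohorts of at most 15 evaluable patients; binding futility at 0/8 and at 1/11 or fewer unconfirmed responses; efficacy at 4/15 or more confirmed; Beta(0.5, 0.5) prior; futility rate 0.05 with threshold 0.20; efficacy rate 0.15 (text and SAP; Protocol Table 11-1 prints 0.17) with threshold 0.80.

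**Assumptions.** Cohorts are independent and accrue fully. Each unconfirmed response is confirmed with probability 15/17, from the documents' pairing of 15% confirmed with 17% unconfirmed. At least two cohorts must qualify, since a homogeneity test needs two.

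**1. The plan's boundaries reproduce.** The posterior is Beta(0.5 + r, 0.5 + n − r).

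- P(θ ≤ 0.05) is 0.64 at 0/8 (stop) and 0.15 at 1/8 (continue).
- P(θ ≤ 0.05) is 0.22 at 1/11 (stop) and 0.04 at 2/11 (continue).
- P(θ > 0.15) is 0.726 at 3/15 (no claim) and 0.892 at 4/15 (claim). With 0.17 the values are 0.647 and 0.843, so the boundary is the same.

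**2. Floor of the pooled point estimate.** 2/15 = 13.3% fails the filter and 3/15 = 20.0% passes. A pool of complete cohorts, each at 20.0% or more, cannot be below 20.0%. Under the SAP's count the floor is 4/15 = 26.7%. If a qualifying cohort closes early for slow accrual, the floor is still 15%.

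**3. The interval has no such floor.** At 6/30 the one-sided 95% exact lower limit is 9.1%, and the SAP's 95% credible interval is 8.8% to 36.7%. At 8/30 the exact lower limit is 14.0%.

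**4. How often a pool appears at a common true confirmed rate of 15%.** Enumerating the 8/11/15 path for one cohort gives a qualifying probability of 0.3585 (3 or more) or 0.1724 (4 or more). Then P(at least 2 of 4) = 1 − (1 − s)^4 − 4s(1 − s)^3:

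- s = 0.3585: 1 − 0.169 − 0.379 = 0.452
- s = 0.1724: 1 − 0.469 − 0.391 = 0.140

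Simulation gives the mean of the reported pool:

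| Filter | Pool reported | Mean pooled ORR | Mean all-cohort ORR |
|---|---|---|---|
| 3/15 or more (Protocol) | about 45% | 24.7% | 14.6% |
| 4/15 or more (SAP) | about 14% | 29.9% | 14.6% |

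Adding the Fisher test at 0.3 changes little: with the Protocol filter, 44.1% of trials and a mean of 24.6%.

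**5. Other true rates (Protocol filter, Fisher test applied).** All at 10%: pool reported in 12.2% of trials, mean 22.8%, against an all-cohort mean of 9.5%. All at 5%: reported in about 0.5% of trials, mean 21.1%, against 4.7%. With no activity worth pursuing, the usual outcome is therefore no overall estimate.

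**6. One data set.** For 0/8, 0/8, 3/15 and 3/15, the Protocol rule gives 6/30 = 20.0%; all cohorts give 6/46 = 13.0%. For 0/8, 0/8, 4/15 and 4/15, which passes either filter, the figures are 8/30 = 26.7% and 8/46 = 17.4%.

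**The case against.** **No decision rests on the pool.** Efficacy is claimed cohort by cohort at 4/15. The pooled analysis is additional and has no success threshold, and Part B is exploratory without formal hypothesis testing. This stands, and it limits the weight of the point. It does not remove overall activity from the primary objective.

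**The selection is disclosed, and every cohort is reported.** A reader could add up the numerators and denominators. That is true, but the plan neither asks for the sum nor requires the pool to be marked as selected on response.

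**The pool may never arise.** SAP 4.3 refers to the futility of the Part B cohorts. If that covers them all, the upward bias is moot and what remains is the missing overall figure.

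**An all-cohort rate has its own bias.** Binding futility leaves inactive cohorts with 8 or 11 patients, so they get less weight. At equal true rates of 15% the all-cohort mean is 14.6%. At 5/5/25/25% (average 15%) it is 16.7%, and at 0/0/30/30% it is 19.2%. It also averages across tumour types, which the protocol avoids when rates differ. This stands, and is why the all-cohort rate should be descriptive and not replace the cohort results.

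**A stronger reading that the documents do not support.** A reader might infer that the overall question can only be answered as active or not at all. Only the point estimate has a floor. Applying the plan's own criterion, P(θ > 0.15) ≥ 0.80, to the smallest Protocol pool of 6/30 gives 0.786, which falls short. Under the SAP's count every pool would pass, but the plan does not apply this criterion to a pool at all. Nor does SAP section 9 forbid an overall figure: it says by cohort, not by cohort only, and SAP 17.1.3 still provides overall reporting under homogeneity.

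**Conclusion.** The point holds in a limited form. The only overall confirmed ORR in the plan is conditional on its cohorts having shown a confirmed rate of at least 15%. In the efficacy population with complete cohorts, its point estimate is at least 20.0% (Protocol) or 26.7% (SAP), and neither planned interval accounts for the selection. At a common true rate of 15%, the reported pool averages about 10 points too high under the Protocol filter (24.7 − 15 = 9.7) and about 15 under the SAP count (29.9 − 15 = 14.9). Otherwise there is no overall estimate, and SAP 4.3 suggests that this may be the actual case.

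These sizes rest on the 15/17 confirmation assumption, full accrual, equal true rates and a minimum of two qualifying cohorts. The 20.0% and 26.7% floors are not strict in the ITT repeat, where replacement of non-evaluable patients can take a cohort above 15. The per-cohort efficacy claims are not affected.

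**What to change.** In Protocol 11.6.2 and 11.6.4 and SAP sections 9 and 17.1.3:

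1. Always report, beside the by-cohort results, a descriptive confirmed ORR with its interval in all evaluable Part B patients from all four cohorts, including futile cohorts and those below 15%.
2. Keep the homogeneity-gated pool, but label it *pooled in cohorts selected for response* and state that it is not to be read as the basket's overall activity.
3. State that the all-cohort rate mixes tumour types and is weighted by futility stopping: slightly low when true rates are equal, high when they differ as in the examples above. The equally weighted mean of the four cohort rates could be added. It removes the sample-size weighting but is itself pulled down by early stopping, because a cohort stopped at 0/8 counts as 0% whatever its true rate.
4. While editing SAP 17.1.3, reconcile the 15% filter with the count of at least 4 responders, since 3/15 = 20.0% also meets 15%.

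The cost is wording and one table column. No new data and no change in conduct are needed. The overall figure will usually look less favourable than the selected pool.

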### 11.6.3. Interim analyses

#### Part A

No formal interim analysis will be performed during the dose-optimization part; review of ongoing data will be done when dose increase, repeat or decrease is to be decided at DSMC meetings.

#### Part B

There will be two interim futility analyses in each cohort. The cut-off for the futility analyses is defined as the time when the last ongoing patient from the first 8/11 evaluable patients has at least 2 post-baseline tumor assessments or prematurely discontinued.

No formal interim analysis will be performed during the futility monitoring. Only the number of patients with, at least, unconfirmed responses as per RECIST v1.1 and/or GCIG criteria (if applicable) will be checked vs. the futility boundaries in each cohort independently.

Bayesian posterior probability of the unconfirmed objective rate will be used for the early stopping rules for futility.

A general confirmed response rate of 15% is considered as promising, justifying further development. This corresponds to approximately 17% unconfirmed response rate. On the other hand, 5% is considered to be the general futility response rate (unconfirmed).

Assuming a probability confidence threshold for futility stopping of 20%, and a maximum sample size of 15 patients by cohort, the futility stopping boundaries are defined for each cohort as follows:

- 0 unconfirmed response out of 8 evaluable patients for the first interim analysis and
- $\leq 1$  unconfirmed response out of 11 evaluable patients for the second interim analysis.

Consequently, if no unconfirmed objective response is documented as per RECIST v1.1 and/or GCIG criteria (if applicable) after the 8th evaluable patient is assessed, futility will then be concluded and the recruitment will be stopped in the corresponding cohort. In case at least one unconfirmed response is documented in the first 8 evaluable patients, recruitment shall continue up to 11 evaluable patients and a second futility analysis will be conducted. If at least two unconfirmed responses are documented in the first 11 evaluable patients, the recruitment will continue up to 15 evaluable patients; otherwise the recruitment will be stopped. The early stopping for futility is binding.

### 11.6.4. Final analysis

The final analysis will be performed within one year of the End of the Main study period (which lasts until 18 months after LPI or 60 days after last LPLV, whichever occurs first).

Data collected after the Main study period for patients entering the Extended study period, will be summarized using descriptive statistics and included in an addendum to the Final CSR.

The main study results will be presented separately for both study parts. An exploratory analysis will be conducted by pooling demographics, baseline characteristics and safety, data from both study parts. In addition, if homogeneity tests allow, and any specific cohort population is adequately represented in Part A, efficacy data from both study parts may be pooled exploratory, as appropriate.

In Part B, according to the Bayesian posterior probability used in each non-futile cohort at the final efficacy assessment conducted in the 15 evaluable patients, the first proof of efficacy will be claimed if at least four confirmed responses are reported in these 15 evaluable patients. This efficacy boundary was derived assuming a confirmed ORR of 15% and a probability confidence threshold of efficacy of 80%.

A homogeneity test of the primary endpoint will be conducted in the non-futile cohorts showing a confirmed response rate of at least 15%. In case of homogeneous response rates across the cohorts, efficacy data will be pooled and all the efficacy endpoints will be reported overall and by cohort. Otherwise, the efficacy will

be reported by cohort only. The efficacy of the futile cohorts and of the cohorts with less than 15% response rate will be reported separately.

All other endpoints such as demographics, baseline characteristics, safety, PK, PDy, etc. will be presented overall and for each cohort.

